3. GENERAL CONSIDERATIONS FOR DATA ANALYSES

Analysis results will be presented using descriptive statistics. For categorical variables, the number and percentage of subjects in each category will be presented; for continuous variables, the number of subjects (n), mean, standard deviation (SD) or standard error (SE), median, first quartile (Q1), third quartile (Q3), minimum, and maximum will be presented.

All statistical tests will be 2-sided and performed at the 5% significance level unless otherwise specified in Section 6.1.

Data collected in the study will be presented in by-subject listings for all subjects in the Safety Analysis Set, unless otherwise specified. All by-subject listings will be presented by subject identification (ID) number in ascending order, unless otherwise specified.

3.1. Analysis Sets

Analysis sets define the subjects to be included in an analysis. Analysis sets and their definitions are provided in this section. The number of subjects eligible for each analysis set will be provided. Subjects who were excluded from each analysis set will be summarized or provided in a by-subject listing with reasons for exclusion by analysis set.

3.1.1. All Randomized Analysis Set

All Randomized Analysis Set includes all subjects randomized in the study after screening. All analyses based on the All Randomized Analysis Set will be performed according to the treatment subjects were randomized to receive.

3.1.2. Full Analysis Set

The Full Analysis Set (FAS) includes all subjects who were randomized into the study and received at least 1 dose of study drug. Subjects are grouped within the FAS by the treatment group to which they were randomized.

This is the primary analysis set for efficacy analyses.

3.1.3. Safety Analysis Set

The Safety Analysis Set includes all subjects who received at least 1 dose of study drug. Subjects are grouped according to the treatment they actually received.

This is the primary analysis set for safety analyses.

3.1.4. Pharmacokinetic Analysis Set

The Pharmacokinetic (PK) Analysis Set includes all subjects who were randomized into the study, received at least 1 dose of study drug, and have at least 1 nonmissing concentration value for the corresponding analyte in plasma. The analyte of interest may include SOF, GS-566500, GS-331007, or VEL. The PK analysis set will be used for analyses of general PK.

3.1.5. PK Substudy Analysis Set

The PK Substudy Analysis Set includes all subjects who are enrolled in the PK substudy, have been administered at least 1 dose of study drug, and have at least 1 nonmissing postdose concentration value for the corresponding analyte in plasma. The analytes of interest may include SOF, GS-566500, GS-331007, or VEL. The PK Substudy Analysis Set will be used for intensive PK profiles of these analytes.

3.2. Subject Grouping

For analyses based on the All Randomized Analysis Set or FAS, subjects will be grouped according to the treatment to which they were randomized. For analyses based on other analysis sets, such as the Safety Analysis Set, subjects will be grouped according to the actual treatment received. The actual treatment received is defined as the randomized treatment except for subjects who received treatment that differed from the randomized treatment for the entire treatment duration. In this case, the actual treatment received is defined as the treatment received for the entire treatment duration.

3.3. Strata and Covariates

Subjects will be randomly assigned to treatment groups via the interactive web response system (IWRS) in a 1:1 ratio using a stratified randomization schedule. Stratification will be based on the following variables:

- Cirrhosis status (presence versus absence)
- HCV genotype (genotype 1 versus 2).

3.4. Examination of Subject Subsets

Subsetting of subjects based on randomization stratification factors will be explored for subgroup analyses. If there are discrepancies in stratification factor values between the IWRS and the clinical database, the values recorded in the clinical database will be used for analyses.

Other subject subsets will also be explored for the primary efficacy endpoint (SVR12), including the following:

- age (< 65 years, \geq 65 years)
- sex (male, female)
- baseline body mass index (BMI) (< 25 kg/m², \geq 25 kg/m²)
- HCV genotype/subtype (1 [1a, 1b, 1 other], 2)
- Number of prior DAAs (1, 2, 3, >3)

- Number of prior HCV treatment regimens (1, 2, 3, 4, 5, >5)
- Prior DAAs (NS5A only, NS5A + NS5B, NS5A + NS3, NS5A + NS5B + NS3, NS5B only, NS5B + NS3)
- cirrhosis (cirrhosis, absence of cirrhosis, missing)
- IL28B genotype (CC, non-CC; with non-CC further broken down to CT, TT)
- baseline HCV RNA (< 800,000 IU/mL, \geq 800,000 IU/mL, and $< 5 \log_{10}$ IU/mL, $\geq 5 \log_{10}$ IU/mL)
- baseline alanine aminotransferase (ALT) ($\leq 1.5 \times$ upper limit of normal range (ULN), $> 1.5 \times$ ULN)
- most recent HCV treatment response (non-responder, relapse/breakthrough, early treatment discontinuation, met a virologic stopping rule not otherwise listed, or unknown)
- study treatment status (completed study treatment, discontinued study treatment)
- adherence to study regimen (< 80%, \geq 80%)

3.5. Multiple Comparisons

The SVR12 rate for genotype 1 patients in each of the two treatment groups will be compared to the historical control rate of 50% using two-sided exact one-sample binomial test with the Bonferroni correction (each at significance level 0.025).

Adjustments for multiplicity will not be made in genotype 2 subjects because no statistical testing will be performed for those subjects.

No between-treatment comparison will be performed for this study.

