8.5. Efficacy Analysis

8.5.1. Primary Analysis

The primary efficacy endpoint for this study will be the proportion of subjects with SVR12, defined as HCV RNA < LLOQ 12 weeks after cessation of treatment. The primary analysis will be performed after all randomized and treated subjects have been followed through 12 weeks posttreatment or discontinued from study.

A point estimate with a two-sided 95% exact confidence interval using the binomial distribution (Clopper-Pearson method) will be constructed for the SVR12 rate by treatment group.

Genotype 1 Subjects

In the primary efficacy analysis, the SVR12 rate for genotype 1 patients in each of the two treatment groups will be compared to the historical control rate of 50% using two-sided exact one-sample binomial test with Bonferroni alpha adjustment (each at significance level 0.025): ie, for each treatment group, the hypothesis for superiority is as follows:

- H_0 : SVR12 rate = 50%
- H_1 : SVR12 rate \neq 50%

The 50% SVR null rate is derived from SVR rates of 43% (59/137) and 59% (57/96) for treatment naive patients with genotype 1 HCV infection and high viral loads treated with PEG IFN and RBV for 48 weeks cited in the Japanese package inserts for REBETOL® Capsules 200 mg (MSD, July 2015, 19th version) and COPEGUS® Tablets 200 mg (Chugai Pharmaceuticals, July 2015, 6th version,) respectively. The weighted average rate then is 50% $((59+57)/(137+96) = 50\%)$.

It is important to note that this historical control rate is a conservative estimate. Because there are no currently available IFN-free treatment options for these subjects and because many of these subjects will have a history of treatment failure with IFN-based therapy and/or medical comorbidities precluding the use of IFN, the actual response rate of this population would likely be much lower than 50%.

Genotype 2 Subjects

No statistical hypothesis testing will be performed in genotype 2 subjects. A point-estimate with two-sided 95% exact confidence interval using the binomial distribution (Clopper-Pearson method) will be constructed for the SVR12 rates.

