8.8. Sample Size

Approximately 110 subjects will be randomized in this study with approximately 90 subjects with genotype 1 HCV infection and approximately 20 subjects with genotype 2 HCV infection. Due to the limited number of genotype 2 subjects in this study, the sample size justification will be based on genotype 1 subjects only.

A sample size of 45 genotype 1 subjects in each treatment group will provide over 90% power to detect at least 27% improvement in SVR12 rate from the historical control rate of 50% using a two-sided exact one-sample binomial test at significance level of 0.025.

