1.3. Sample Size and Power

Approximately 110 subjects will be randomized in this study with approximately 90 subjects with genotype 1 HCV infection and approximately 20 subjects with genotype 2 HCV infection. Due to the limited number of genotype 2 subjects in this study, the sample size justification will be based on genotype 1 subjects only.

A sample size of 45 genotype 1 subjects in each treatment group will provide over 90% power to detect at least 27% improvement in SVR12 rate from the historical control rate of 50% using a two-sided exact one-sample binomial test at significance level of 0.025.

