6.1.2. Statistical Hypothesis for the Primary Efficacy Endpoint

In the primary efficacy analysis, the SVR12 rate for genotype 1 subjects in each of the two treatment groups will be compared to the performance goal of 50% using a 2-sided exact 1-sample binomial test at the 0.025 significance level. The null (H_0) and alternative (H_1) hypotheses used to assess superiority of SOF/VEL+RBV relative to the performance goal of 50% are:

- H_0 : SVR12 rate = 50%
- H_1 : SVR12 rate \neq 50%

The 50% SVR null rate is derived from SVR rates of 43% (59/137) and 59% (57/96) for treatment naive patients with genotype 1 HCV infection and high viral loads treated with PEG IFN and RBV for 48 weeks cited in the Japanese package inserts for REBETOL® Capsules 200 mg (MSD, July 2015, 19th version) and COPEGUS® Tablets 200 mg (Chugai Pharmaceuticals, July 2015, 6th version), respectively. The weighted average rate then is 50% ((59+57)/(137+96) = 50%).

It is important to note that this historical control rate is a conservative estimate. Because there are no currently available IFN-free treatment options for these subjects and because many of these subjects will have a history of treatment failure with IFN-based therapy and/or medical comorbidities precluding the use of IFN, the actual response rate of this population would likely be much lower than 50%.

No statistical hypothesis testing will be performed in genotype 2 subjects.

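### Holm's step-down procedure would be at least as powerful as the planned Bonferroni split, within the same 0.05 family-wise bound (minor improvement, not an error)

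*SAP*

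**What the plan says.** SAP 3.5 compares each genotype 1 arm with a fixed 50% rate "with the Bonferroni correction (each at significance level 0.025"). Protocol 8.5.1 specifies the same rule, a "two-sided exact one-sample binomial test with Bonferroni alpha adjustment (each at significance level 0.025"), and the synopsis repeats it. SAP 3 sets a general default: "All statistical tests will be 2-sided and performed at the 5% significance level unless otherwise specified in Section 6.1". SAP 6.1.2 supplies the exception, "using a 2-sided exact 1-sample binomial test at the 0.025 significance level", so the SAP is consistent on the level. Neither document has a step-down rule or passes alpha from one test to the other.

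The family has exactly two members. SAP 3.5 rules out a between-arm comparison, and genotype 2 is estimated without a test.

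The power statement in SAP 1.3 and Protocol 8.8 is for one arm: "A sample size of 45 genotype 1 subjects in each treatment group will provide over 90% power". No target is given for the two arms together.

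**The concern.** The primary analysis draws a separate conclusion for each treatment duration. Under plain Bonferroni each arm must clear 0.025 whatever the other arm shows. If one arm has already rejected at 0.025, only one hypothesis remains, and it can be tested at 0.05 without breaching the family-wise bound. Holm's procedure does this. It rejects everything Bonferroni rejects and sometimes more, and it holds the family-wise error at 0.05 under any dependence between the tests.

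What is at stake is the second arm's conclusion. An arm with 30/45 responders fails under the plan even when the other arm has clearly succeeded. The usual reason to keep Bonferroni, simultaneous confidence intervals that match the tests, does not apply here. SAP 6.1.3 plans an unadjusted 95% Clopper-Pearson interval per arm, and at 30/45 that interval is 51.0% to 80.0%. It excludes 50% although the 0.025 test does not reject.

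**Working it through.** **Inputs**
- Null rate 50%: SAP 6.1.2, "The weighted average rate then is 50" per cent; (59+57)/(137+96) = 116/233 = 0.498.
- Alternative 77%: SAP 1.3, "at least 27% improvement in SVR12 rate from the historical control rate of 50" per cent, read as 50 + 27 percentage points.
- n = 45 genotype 1 subjects per arm (SAP 1.3).
- Two-sided exact binomial test, 0.025 per arm (SAP 6.1.2).
- Independent counts, because the arms are separately randomized. This enters the power figures only; Holm's error control does not need it.

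**Rejection thresholds.** Under Binomial(45, 0.5), 31/45 gives two-sided p = 0.0161, 30/45 gives p = 0.0357 and 29/45 gives p = 0.0725. The upper threshold is therefore 31 at 0.025 and 30 at 0.05.

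**The plan's own figure.** P(X ≥ 31) at 77% is 0.9252. This meets the stated power, "will provide over 90% power to detect at least 27% improvement in SVR12 rate".

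**Bonferroni against Holm at 77% in both arms.** Let a = 0.9252 be the chance of rejecting at 0.025 and b = P(X ≥ 30) = 0.9614 the chance of rejecting at 0.05.
- Per arm, Bonferroni: a = 92.5%.
- Per arm, Holm: a + (b − a)a = 0.9252 + 0.0362 × 0.9252 = 95.9%.
- Both arms, Bonferroni: a² = 85.6%.
- Both arms, Holm: b² − (b − a)² = 0.9243 − 0.0013 = 92.3%.
- At least one arm, either rule: 1 − (1 − a)² = 99.4%.

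**Other true rates** (all assumed, to show the range)

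| True rate, arm 1 / arm 2 | Both succeed, Bonferroni | Both succeed, Holm |
|---|---|---|
| 70% / 70% | 40.3% | 54.4% |
| 71% / 71% | 47.5% | 61.6% |
| 70% / 90% | 63.5% | 74.6% |
| 77% / 77% (design) | 85.6% | 92.3% |
| 85% / 85% | 99.7% | 99.9% |
| 90% / 90% | about 100% | about 100% |

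**Attained error**
- Both nulls true: 1 − (1 − 0.0161)² = 3.19% under either rule.
- One null true and the other arm certain to reject: 1.61% under Bonferroni, 3.57% under Holm. Both are below 5%.

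**Which results change.** The thresholds differ by one responder. For superiority, the conclusion changes only when one arm has exactly 30/45 and the other at least 31/45. This leaves aside a rejection in the wrong direction in the other arm (14/45 or fewer), which is negligible at the rates in the table. At n = 40, 43, 44, 46 and 47 the thresholds also differ by one responder.

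**The case against.** The strongest case for leaving the plan alone is that nothing in it is wrong. Bonferroni is valid and prespecified, and its one stated power target is met. A reader might infer from the 85.6% that the trial is underpowered. The documents do not support that, because they set no target for both arms together.

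A reader might also take the 71% in Protocol 1.4 as a plausible rate for this trial and quote the larger gain there. That figure belongs to 24 weeks of ledipasvir/sofosbuvir, a different retreatment regimen cited to show unmet need, so the row is illustrative only. For SOF/VEL plus ribavirin, Protocol 1.2.3.3.4 reports no virologic failures among genotype 1 and 2 subjects who completed 24 weeks. That points to the high range, where Holm adds almost nothing, but it covers completers of the longer duration after earlier SOF/VEL and does not settle the 12-week arm.

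The rescued result, 30/45 or 66.7%, is modest and lies below that 71%. This bears on how much the extra rejection is worth, not on whether it is valid.

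Nor is the overall error rate simply unchanged. The 0.05 bound is, but attained error with one true null more than doubles (1.61% to 3.57%), and one arm's conclusion comes to depend on the other's.

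Finally, a late change to a primary success rule in an open-label trial judged against a fixed rate would invite challenge. That objection stands and governs the timing of the fix.

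**Conclusion.** The point holds as a minor efficiency gain and not as an error. At the design alternative Holm adds 3.3 points of power per arm and 6.7 points for success in both arms, adds nothing for at least one arm, and keeps the 0.05 family-wise bound. At 85% in both arms the gain is about 0.1 points per arm and 0.2 points for both. The power figures assume 45 genotype 1 subjects per arm, independent arms and the exact two-sided test. Every rate other than 77% is an assumption.

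**What to change.** In SAP 3.5 and 6.1.2, state that the two genotype 1 tests use Holm's procedure at a family-wise two-sided 0.05: the smaller p-value is compared with 0.025 and, if it rejects, the other with 0.05. Make the same change in Protocol 8.5.1 and the synopsis for consistency. If the protocol is not amended, record the departure in SAP 6.4, which now declares no changes from the protocol-specified efficacy analyses.

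Date the change before any SVR12 results are tabulated. Finalizing the SAP before database finalization (SAP 1) is not enough, because the study is open-label.

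The cost is a short wording change in the SAP. A matching protocol amendment would also need IRB or IEC approval (Protocol 9.2.1). No subjects or data are added, and the sample size and the power statement stand.

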3.6. Missing Data and Outliers

3.6.1. Missing Data

In general, missing data will not be imputed unless methods for handling missing data are specified.

For missing last dosing date of study drug, imputation rules are described in Section 3.8.1. The handling of missing or incomplete dates for adverse event (AE) onset is described in Section 7.1.5.2, and for prior and concomitant medications in Section 7.4.

For analyses of categorical HCV RNA data, missing posttreatment HCV RNA data will have the missing data imputed. Missing on-treatment HCV RNA will have the missing data imputed up to the time of the last dose (for on-treatment displays). If the study day associated with the last

dosing date is greater than or equal to the lower bound of a visit window, and the value at the visit is missing, the value will be imputed. If the study day associated with the last dosing date is less than the lower bound of a visit window then the on-treatment value at that visit will remain missing.

If an HCV RNA data point is missing and is preceded and followed in time by values that are “< lower limit of quantitation (LLOQ) target not detected (TND),” then the missing data point will be set to “< LLOQ TND.” If a data point is missing and preceded and followed by values that are “< LLOQ detected,” or preceded by “< LLOQ detected” and followed by “< LLOQ TND,” or preceded by “< LLOQ TND” and followed by “< LLOQ detected,” then the missing value will be set to “< LLOQ detected.” In these situations the data point will be termed a bracketed success; otherwise, the data point will be termed a bracketed failure (ie, \geq LLOQ detected). If a data point is missing and is not bracketed, the missing data point will also be termed a failure (ie, \geq LLOQ detected) except for SVR24, which will be imputed according to SVR12 status. Success for SVR12 who have no further HCV RNA measurements collected will be counted as a success for SVR24 due to the high correlation between these 2 endpoints.

For the analyses of continuous HCV RNA efficacy data, when and only when a missing HCV RNA value is imputed as < LLOQ TND or < LLOQ detected according to the imputation rule described above, the corresponding continuous value will be imputed to LLOQ – 1 IU/mL. No other imputation will be performed for continuous HCV RNA data.

For health-related quality of life (HRQoL) data including 36-Item Short Form Health Survey (SF-36), Chronic Liver Disease Questionnaire (CLDQ-HCV), Fatigue Index (FACIT-F), and Work Productivity and Activity Impairment Questionnaire: Hepatitis C, v2.0 (WPAI: Hepatitis C), missing data will not be imputed.

3.6.2. Outliers

Outliers will be identified during data management and data analysis processes, but no sensitivity analyses will be conducted. All available data will be included in the data analysis.

3.7. Data Handling Conventions and Transformations

By-subject listings will be presented for all subjects in the Safety Analysis Set and sorted by subject ID number, visit date, and time (if applicable) unless otherwise specified. Data collected on log forms, such as AEs, will be presented in chronological order within subject.

Age (in years) on the date of the first dose of study drug and sex at birth will be used for analyses and presentation in listings.

If a subject was not dosed with study drug, then the date the informed consent was signed will be used instead of the first dose date of study drug. For some countries, only birth year is collected on the case report form (CRF). In those cases, “01 January” will be used for the unknown birth day and month for the purpose of age calculation, unless age is captured on the CRF.

Non-pharmacokinetics (PK) data that are continuous in nature but are less than the lower limit of quantitation or above the upper limit of quantitation will be imputed as follows:

- A value that is one unit less than the limit of quantitation will be used for calculation of descriptive statistics if the datum is reported in the form of “ $< x$ ” (where x is considered the limit of quantitation). For example, if the values are reported as < 50 and < 5.0 , values of 49 and 4.9, respectively, will be used for calculation of summary statistics. An exception for this rule is any value reported < 1 . For the values reported as < 1 or < 0.1 , values of 0.9 or 0.09 will be used for calculation of summary statistics.
- A value that is one unit above the limit of quantitation will be used for calculation of descriptive statistics if the datum is reported in the form of “ $> x$ ” (where x is considered the limit of quantitation). Values with decimal points will follow the same logic as above.
- The limit of quantitation will be used for calculation of descriptive statistics if the datum is reported in the form of “ $\leq x$ ” or “ $\geq x$ ” (where x is considered the limit of quantitation).

The COBAS® AmpliPrep/COBAS® TaqMan® HCV Quantitative Test v2.0 was used to determine HCV RNA results in this study. The LLOQ of the assay is 15 IU/mL.

When the calculated HCV RNA value is within the linear range of the assay, then the result will be report as “ $<<$ numeric value $>>$ IU/mL.” This result is referred to in this document as the numeric result or as “ \geq LLOQ detected” for categorical result.

When HCV RNA is not detected, the result is reported as “No HCV RNA detected” or “target not detected”. This result will be referred to in this document as “ $<$ LLOQ target not detected” or “ $<$ LLOQ TND.”

When the HCV RNA IU/mL is less than LLOQ of the assay, the result is reported as “ < 15 IU/mL HCV RNA detected.” This result will be referred to in this document as “ $<$ LLOQ detected.”

The overall category of HCV RNA $<$ LLOQ includes “ $<$ LLOQ TND” and “ $<$ LLOQ detected.”

For numerical HCV RNA data, values below LLOQ will be set to the LLOQ – 1 IU/mL. HCV RNA values returned as “NO HCV RNA detected” will also be set to LLOQ – 1 IU/mL.

For selected analyses, HCV RNA data (IU/mL) will be transformed to the logarithmic (base 10) scale (\log_{10} IU/mL).

Natural logarithm transformation will be used for plasma/blood concentrations and analysis of PK parameters. Plasma concentration values that are below the lower limit of quantitation (BLQ) will be presented as “BLQ” in the concentration data listing.

